6. STUDY ENDPOINTS

The primary endpoints are:

- Safety and tolerability of OMS721 as assessed by AEs, vital signs, clinical laboratory tests, and ECGs

The secondary endpoints are:

- 24-hour urine protein change from baseline to 12 weeks
- Urine albumin/creatinine ratio change from baseline to 12 weeks
- Corticosteroid dose needed to maintain stable renal function (Cohort 1)
- PK concentration and PK parameters of OMS721
- PD measure of inhibition of *ex vivo* lectin pathway activation

The exploratory endpoints are:

- Urine protein/creatinine ratio by disease
- Serum creatinine by disease
- eGFR by disease calculated by the MDRD equation, the CKD-EPI equation using serum creatinine, the CKD-EPI equation using cystatin C, and the CKD-EPI equation using creatinine – cystatin C
- Occurrence of ADA and Nab
- Urine inflammatory markers by disease
- Duration of therapeutic response, if observed, defined as the number of the longest consecutive weeks that 24-hour urine protein < 50% of the baseline for up to 104 weeks (Cohort 3 only)

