For all subjects in Cohort 1 and Cohort 2, the study will consist of screening (4 weeks), treatment (12 weeks), and follow-up (6 weeks) periods.

For subjects in Cohort 3, the study will consist of screening (4 weeks), initial treatment (12 weeks) and initial follow-up (6 weeks). Cohort 3 subjects who have 24-hour urine protein $\geq 50\%$ of baseline or $> 1000\text{ mg}/24\text{ hours}$ at the end of the initial follow-up period (6-week follow-up visit) may elect to receive open-label OMS721 370 mg IV once weekly for 12 additional weeks. Follow-up for all Cohort 3 subjects will be 104 weeks from the first dose of study drug.

Subjects will have two screening visits within a 28-day screening period. Within the screening period and before the first study drug dose, consented subjects will provide three urine samples

CONFIDENTIAL

No use, disclosure or reproduction outside of Omeros without prior written authorization

(collected once daily) on each of two three-consecutive-day periods to establish baseline values of the albumin/creatinine ratio and protein/creatinine ratio. In addition, the subjects will provide one 24-hour urine protein sample to establish baseline values and confirm eligibility.

During the initial 4 weeks of treatment, Cohort 1 subjects will be maintained on their stable pre-study dose of corticosteroids. This initial 4-week treatment period will allow assessment of whether OMS721 can improve measures of renal function when administered to subjects with steroid-dependent disease when co-administered with corticosteroids. Investigators will be instructed to maintain subjects' dose of corticosteroids during the initial 4-week period unless an increase in corticosteroid dose is medically indicated.

At the end of the initial 4-week treatment period, Cohort 1 subjects will undergo corticosteroid taper over 4 weeks. The target will be a taper to ≤ 6 mg prednisone (or equivalent dose) daily. The taper schedule will be at the discretion of the Investigator. Over this period, the taper will be discontinued in subjects who have deterioration of renal function, as determined by the Investigator. Subjects will be treated with OMS721 through the corticosteroid taper and complete 12 weeks of treatment. The taper of steroids and OMS721 treatment will permit assessment of whether OMS721 allows a decrease in the dose of corticosteroid required to maintain stable renal function.

[figure not shown]

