7.3.2. Secondary Endpoint

The secondary endpoints are:

- Proteinuria from baseline to 12 weeks assessed by 24-hour urine protein collection by disease
- Urine albumin/creatinine ratio by disease
- Corticosteroid dose needed to maintain stable renal function by disease (Cohort 1)
- PK
- PD

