10.1.9. Follow-Up Visit 1 (Day 85; +/- 3 days)

One week after the last dose of study drug, the following procedures and assessments will be performed:

1. Vital signs will be taken including BP, pulse rate, RR, and temperature (after at least 5 minutes of rest).
2. AEs and concomitant medications, including corticosteroid dose (if applicable) will be recorded.
3. Laboratory samples will be collected for:
 - Hematology, chemistry, coagulation, cystatin C
 - Urinalysis
 - Urine for inflammatory biomarkers
 - Serum or urine pregnancy test in women of childbearing potential. If the test result is positive then the subject will be followed for outcome of the pregnancy

CONFIDENTIAL

No use, disclosure or reproduction outside of Omeros without prior written authorization

- Serum PK samples
 - Serum PD sample
 - Serum ADA sample
4. For three days prior to Follow-Up Visit 1, three once daily first void urine samples for urine albumin/creatinine ratios will be collected and brought for analysis at this visit.
 5. For Cohort 3 subjects only, subjects will be provided with supplies to collect 24-hour urine samples in the week prior to next Follow-Up Visit. The investigative site will call the subject one week prior to the next follow-up visit to remind the subject to collect the 24-hour urine sample.
 6. At Follow-Up Visit 1, subjects will be provided with supplies to collect first void urine samples for urine albumin/creatinine and protein/creatinine ratios on three mornings prior to Follow-Up Visit 2.

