19. APPENDICES

19.1. MDRD Equation

MDRD Equation when calculating creatinine clearance if the lab uses an Isotope-Dilution Mass Spectrometry (IDMS) method for serum creatinine determination:

$$\text{eGFR (mL/min/1.73 m}^2\text{)} = 175 \times (\text{SCr})^{-1.154} \times (\text{Age})^{-0.203} \times (0.742 \text{ if female}) \times (1.212 \text{ if African American})$$

Note: SCr = Serum Creatinine measurement should be mg/dL.

19.2. Study Schedule of Events – Cohorts 1, 2, and 3 First 12 Week Treatment Period

Period	Screening		Treatment (12 Weeks)											Follow-Up (6 Weeks)		Cohort 3 Extended Follow Up
Visit	SCR 1	SCR 2	T1			T2, T3	T4	T5	T6, T7	T8	T9	T10, T11	T12	FU 1	FU 2	FU 3-FU 9
Day	-28	-14	1	2	4	8,15	22	29	36, 43	50	57	64,71	78	85	120	176, 267, 358, 449, 540, 631, 722
		(+/- 7)				(+/ - 2)								(+/- 3)		(+/- 14)
Week	-4	-1	1			2-3	4	5	6-7	8	9	10-11	12	13	18	26,39,52,65,78, 91,104
Informed Consent, Medical History, & Physical Examination	X															
Review of Inclusion/Exclusion Criteria	X	X	X													
Randomization (where applicable)			X													
Assessment of renal function and tapering of corticosteroid dose (where applicable)								X	X	X						
Vital Signs	X	X												X	X	
Vital Signs pre-dose			X			X	X	X	X	X	X	X	X			
Vital Signs post dose: 30 min			X			X	X	X	X	X	X	X	X			
Vital Signs post dose: 1 hr			X													
ECG	X															
ECG pre-dose			X										X			
ECG post dose			X ⁷										X			
Dispense urine collection kit ¹	X	X					X			X			X	X		
Collect Urine Samples from urine collection kit ²		X	X					X			X			X	X	
Dispense supplies for 24-hour Urine protein collection ¹	X													X		X
Collect 24-hour Urine protein samples		X													X	
Urine for inflammatory biomarkers	X						X							X		X
Urinalysis ³	X		X			X	X			X				X		X
Blood Sample Collection: Chemistry, Hematology, Coagulation, Cystatin C ⁴ .	X		X			X	X			X				X	X	X

CONFIDENTIAL**No use, disclosure or reproduction outside of Omeros without prior written authorization**

Period	Screening		Treatment (12 Weeks)											Follow-Up (6 Weeks)		Cohort 3 Extended Follow Up
Visit	SCR 1	SCR 2	T1			T2, T3	T4	T5	T6, T7	T8	T9	T10, T11	T12	FU 1	FU 2	FU 3-FU 9
Day	-28	-14	1	2	4	8,15	22	29	36, 43	50	57	64,71	78	85	120	176, 267, 358, 449, 540, 631, 722
		(+/- 7)				(+/ - 2)								(+/- 3)		(+/- 14)
Week	-4	-1	1			2-3	4	5	6-7	8	9	10-11	12	13	18	26,39,52,65,78, 91,104
Anti- PLA2R ⁵	X															
Calculation of eGFR using the MDRD formula		X														

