5. STUDY DURATION AND VISIT SCHEDULE

5.1. Cohorts 1, 2, and 3 First 12 Week Treatment Period

Period	Screening		Treatment (12 Weeks)											Follow-Up (6 Weeks)		Cohort 3 Extended Follow Up
Visit	SCR 1	SCR 2	T1			T2, T3	T4	T5	T6, T7	T8	T9	T10, T11	T12	FU 1	FU 2	FU 3-FU 9
Day	-28	-14	1	2	4	8,15	22	29	36, 43	50	57	64,71	78	85	120	176, 267, 358, 449, 540, 631, 722
		(+/- 7)				(+/ - 2)							(+/ - 3)			(+/- 14)
Week	-4	-1	1			2-3	4	5	6-7	8	9	10-11	12	13	18	26,39,52,65,78, 91,104
Informed Consent, Medical History, & Physical Examination	X															
Review of Inclusion/Exclusion Criteria	X	X	X													
Randomization (where applicable)			X													
Assessment of renal function and tapering of corticosteroid dose (where applicable)								X	X	X						
Vital Signs	X	X												X	X	
Vital Signs pre-dose			X			X	X	X	X	X	X	X	X			
Vital Signs post dose: 30 min			X			X	X	X	X	X	X	X	X			
Vital Signs post dose: 1 hr			X													
ECG	X															
ECG pre-dose			X										X			
ECG post dose			X										X			
Dispense urine collection kit ¹	X	X					X			X			X	X		
Collect Urine Samples from urine collection kit ²		X	X					X			X			X	X	
Dispense supplies for 24-hour Urine protein collection ¹	X													X	X ¹	X ¹
Collect 24-hour Urine protein samples		X													X	X
Urine for inflammatory biomarkers	X						X							X		X
Urinalysis ³	X		X			X	X			X				X		X

Period	Screening		Treatment (12 Weeks)											Follow-Up (6 Weeks)		Cohort 3 Extended Follow Up
Visit	SCR 1	SCR 2	T1			T2, T3	T4	T5	T6, T7	T8	T9	T10, T11	T12	FU 1	FU 2	FU 3-FU 9
Day	-28	-14	1	2	4	8,15	22	29	36, 43	50	57	64,71	78	85	120	176, 267, 358, 449, 540, 631, 722
		(+/- 7)				(+/ - 2)							(+/ - 3)			(+/- 14)
Week	-4	-1	1			2-3	4	5	6-7	8	9	10-11	12	13	18	26,39,52,65,78, 91,104
Blood Sample Collection: Chemistry, Hematology, Coagulation, Cystatin C ⁴ , Anti- PLA2R ⁵	X		X			X	X			X				X	X	X
Calculation of eGFR using the MDRD formula	X															
Serology for HIV, hepatitis B and hepatitis C	X	X														
Pregnancy Test – females of child bearing potential ⁶	X		X					X			X			X		
Study Drug Administration			X			X	X	X	X	X	X	X	X			
Research Sampling			X			X	X			X						
PK Sampling														X	X	
PK Sampling pre-dose			X			X	X	X	X	X	X	X	X			
PK Sampling post dose: 5 minutes and 2 hours			X													
PK Sampling post dose: 30 min						X		X			X		X			
PK Sampling post dose: 24 hours				X												
PK Sampling post dose: 72 hours					X											
PD Sampling														X	X	

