8.3.3. Efficacy Population

The efficacy population includes all subjects who receive any amount of study drug, and have a baseline and at least one post-baseline 24-hour urine protein.

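### The 24-hour urine protein endpoint is set at 12 weeks, but the first post-baseline collection is at Week 18, off drug, and the visit text and schedules disagree on whether Cohorts 1 and 2 provide it

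*SAP*

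**What the plan says.** **Time point.** SAP 6 lists "24-hour urine protein change from baseline to 12 weeks" as the first secondary endpoint. Protocol 7.3.2 has "Proteinuria from baseline to 12 weeks assessed by 24-hour urine protein collection by disease".

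**Baseline.** Protocol 7.1 provides for a single screening collection in every cohort: "the subjects will provide one 24-hour urine protein sample to establish baseline values and confirm eligibility".

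**Schedules.** The row "Collect 24-hour Urine protein samples" in SAP 5.1 is marked at Screening Visit 2, Follow-Up Visit 2 and the Cohort 3 extended visits. The same row in Protocol 19.2 is marked at Screening Visit 2 and Follow-Up Visit 2; the extended-visit collections are in the text of 10.1.11. Protocol 19.2 is titled "Study Schedule of Events – Cohorts 1, 2, and 3 First 12 Week Treatment Period", and SAP 5.1 has the same scope. Neither table limits the Follow-Up Visit 1 dispensing mark or the Follow-Up Visit 2 collection mark to a cohort.

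**Visit text.** Protocol 10.1.9 (Follow-Up Visit 1, Day 85) says "For Cohort 3 subjects only, subjects will be provided with supplies to collect 24-hour urine samples in the week prior to next Follow-Up Visit". Protocol 10.1.10 (Follow-Up Visit 2, Day 120) lists no 24-hour urine for any cohort.

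**Population.** SAP 8.3.3, like Protocol 13.2.1.2, admits treated subjects who "have a baseline and at least one post-baseline 24-hour urine protein". SAP 9.1 assigns all efficacy data to this population.

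**The concern.** An endpoint needs an observation at the time it names. Here the first secondary efficacy endpoint names 12 weeks, and the plan collects nothing at that time. The only value in the initial period comes after six weeks without drug. It answers a different question: how much effect remains off treatment, not how much there is at the end of treatment.

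The population rule spreads the problem. One missing 24-hour urine removes a subject from the albumin/creatinine, protein/creatinine, eGFR, serum creatinine and steroid-dose summaries as well, although those data come from other samples at other visits. In the randomised cohorts this makes inclusion depend on staying in the study after randomisation. With 10 and 18 planned subjects, losing one or two matters.

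The conflict over Cohorts 1 and 2 also matters, because lupus nephritis, membranous nephropathy and C3 glomerulopathy are enrolled in Cohort 1 only and cannot roll over to Cohort 3.

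**Working it through.** The plan gives no power-based figure to reproduce, since the sample size is empirical. The planned numbers add up: 16 + 10 + 18 = 44. The check is a count of scheduled collections against the visit days.

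**Step 1: is there a 12-week collection?** Days and labels are from Protocol 19.2, windows from SAP Table 2. Weeks elapsed = (day − 1)/7; weeks off drug = (day − 78)/7, because the twelfth dose is on Day 78.

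| Visit | Day | Label | Weeks elapsed | Weeks after last dose | SAP window (days) | 24-hour urine |
|---|---|---|---|---|---|---|
| Treatment Visit 12 | 78 | Week 12 | 77/7 = 11.0 | 0 | 75–81 | none |
| Follow-Up Visit 1 | 85 | Week 13 | 84/7 = 12.0 | 7/7 = 1.0 | 82–102 | none |
| Follow-Up Visit 2 | 120 | Week 18 | 119/7 = 17.0 | 42/7 = 6.0 | 103–148 | marked in both schedules |

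Whether 12 weeks means Day 78 (by label) or Day 85 (by elapsed time), nothing is collected. Protocol 10.1.8 and 10.1.9 agree with the tables on this.

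**Step 2: can the windows supply a value?** The sample is taken in the week before Follow-Up Visit 2, which falls on Day 120 ± 3. The earliest day is 120 − 3 − 7 = 110 and the latest 120 + 3 = 123. Days 110–123 lie wholly within 103–148 and do not touch 75–81 or 82–102. Protocol 13.2.1.1 rules out imputation. Planned 24-hour values at 12 weeks: 0 in every cohort.

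**Step 3: how many Cohort 1 and 2 subjects have any post-baseline value?** Planned total 16 + 10 = 26, and 26/44 = 59%. Let r be the number who roll over and reach the Day 120 collection under Cohort 3 procedures (Protocol 7.1); the documents do not give r.

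- Visit text governs: 26 − r subjects have none. With r = 0 that is all 26, and it always includes every subject with lupus nephritis, membranous nephropathy or C3 glomerulopathy.
- Schedules govern: up to 26 of 26 have one value, six weeks off drug.

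**Step 4: who is lost under either reading?** Protocol 8.3.2 and 10.1.15 give a subject who leaves the study the Follow-Up Visit 1 assessments, which contain no 24-hour urine. Leaving before the Day 120 collection therefore means no post-baseline 24-hour value. By then the subject may have ratios from Days 29, 57 and 85, chemistry and cystatin C from Day 8 on, and in Cohort 1 a steroid dose recorded at each visit.

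**The case against.** The strongest case on the other side has four parts.

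**The analyses run by visit.** SAP 12.6 and Protocol 13.2.5 summarise change at each visit. The synopsis endpoint list and Protocol 11.1 state the 24-hour endpoint without a 12-week limit. The study is descriptive, with safety as its primary endpoint. This stands in part: a Week 18 change can be computed, so it would be wrong to say that the endpoint yields nothing. What has no data is the endpoint at the time both documents give it.

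**The efficacy population is not shown to be empty.** From Protocol 10.1.9 a reader might infer that Cohorts 1 and 2 have no evaluable subjects, or that exactly 26 of 44 lack a value. The documents do not support either. Both schedules mark a Day 120 collection for all three cohorts, and rollover subjects follow Cohort 3 procedures. The list in 10.1.10 omits the 24-hour urine even for Cohort 3, whose re-treatment eligibility is judged on it (Protocol 7.1), so absence from that list proves little. The tables are not decisive either. SAP 5.1 also marks dispensing at Follow-Up Visit 2 without a cohort limit, although Cohorts 1 and 2 finish there. Protocol 10 describes Section 19 as a summary, while SAP 7 points to both the visit text and its own table. This is a contradiction, not proof of missing data.

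**Stopping drug is not leaving the study.** Protocol 8.3.1 asks subjects who stop drug to complete all scheduled visits. This stands: the automatic exclusion applies only to those who leave the study before the Day 120 collection.

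**Cohorts 1 and 2 were already running.** What was collected under earlier protocol versions is not visible. This stands, and it makes any statement that three of the four diseases will have no efficacy result conditional.

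**Conclusion.** The plan is wrong as written on two points and contradicts itself on a third.

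- The 12-week 24-hour urine protein endpoint has no scheduled data in any cohort. The nearest scheduled value is at Day 120, 42 days after the last dose.
- The efficacy population ties every efficacy summary to that one late sample, so a subject who leaves before it is excluded from all of them. This holds under either reading of the documents, assuming only scheduled collections are available.
- On Cohorts 1 and 2 the visit text and the schedules conflict. The number with a post-baseline value ranges from 0 to 26 of 26, depending on which governs and on the unknown number of rollovers. The 59% is a ceiling on the share of planned subjects affected, not an estimate.

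The two documents also place rollovers differently: Protocol 13.2.1 makes them a separate cohort, while SAP 12.1 keeps Cohort 1 and 2 analyses to the initial treatment and follow-up data. This decides where any rollover value would be reported. It does not change the first two conclusions.

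**What to change.** 1. **Population.** In SAP 8.3.3 and Protocol 13.2.1.2, define the efficacy population per endpoint: treated, with a baseline and at least one post-baseline value of the endpoint being analysed. Cost: wording only.
2. **Time point.** In SAP 6 and Protocol 7.3.2, restate the 24-hour endpoint as change to Week 18, six weeks after the last dose. Report the Day 85 albumin/creatinine ratio, already a secondary endpoint, and the Day 85 protein/creatinine ratio as the end-of-treatment proteinuria measures. Correct item 4 of Protocol 10.1.9, which lists only the albumin/creatinine ratio although Treatment Visit 12 dispenses supplies for both. Cost: wording only.
3. **Text against schedules.** Reconcile Protocol 10.1.9 and 10.1.10 with Protocol 19.2 and SAP 5.1 on which cohorts give a 24-hour urine at Day 120. If Cohorts 1 and 2 do not, say so and withdraw the 24-hour endpoint for their non-rollover subjects; item 1 then keeps their other efficacy data. Cost: wording, after the sponsor checks what has been collected so far.
4. **Optional.** Add a 24-hour urine at Day 85 for subjects not yet past that visit, with the kit handed out at Treatment Visit 12 alongside the first-void supplies. The re-treatment schedule already has such a collection one week after its last dose (Protocol 10.1.14 and 19.3). This would restore an end-of-treatment value for those subjects. Cost: one extra home collection each, with no new visit.

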10. Have any significant infection requiring antibiotic treatment at Screening Visit 1.
11. Have a malignancy except for adequately treated and cured basal or squamous cell skin cancer, curatively treated in situ disease, or other cancer from which the patient has been disease-free for ≥ 5 years.
12. Have an expectation of survival of less than 24 months.
13. If female, are pregnant or breastfeeding.
14. Have received any other investigational drug or device or experimental procedures within 30 days of Screening Visit 1.
15. Are an employee of Omeros, the investigative site, a study staff member, or their immediate family member.
16. Have any condition that the Investigator believes would put the subject at risk from participation.
17. For subjects in Cohort 2 and Cohort 3, have received corticosteroids within the 3 months prior to screening. Subjects in Cohort 1 rolling into Cohort 3 must have IgAN and must have discontinued corticosteroids prior to entry into Cohort 3, but the discontinuation may occur at any time prior to Cohort 3 entry.

Investigational Product, Dosage, and Mode of Administration:

[REDACTED]

[REDACTED]

[REDACTED]

Duration of Treatment: 12 weeks for Cohorts 1 and 2; Initially 12 weeks with potential additional treatment for Cohort 3

CONFIDENTIAL

No use, disclosure or reproduction outside of Omeros without prior written authorization

Reference Therapy, Dosage, and Mode of Administration: Intravenous D5W for Cohort 2 and 3 only

Study Endpoints:

1. Safety and tolerability of OMS721 as assessed by AEs, vital signs, clinical laboratory tests, and ECGs
2. Change from baseline in 24-hour urine protein
3. Change from baseline in urine albumin/creatinine ratio by disease
4. Corticosteroid dose required to maintain stable renal function by disease (Cohort 1)

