7.2.1. Rationale for Dose Selection

The dose level of OMS721 370 mg IV in this study inhibits the lectin pathway for approximately one week and provides high levels of lectin pathway inhibition for approximately 4 to 5 days. Prior doses of 4 mg/kg were associated with marked improvement in urinary protein measures in subjects with aHUS, IgA nephropathy, MN, and lupus nephritis. This dose was well tolerated. The fixed dose is within the range of doses provided previously in this study.

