10.1.8. Treatment Visit 10, 11, 12 (Days 64, 71, 78; +/- 2 days)

The following procedures will be performed at Treatment Visits 10, 11, and 12:

Prior to dosing with study drug, the following procedures will be performed:

1. Vital signs including BP, pulse rate, RR, and temperature (after at least 5 minutes of rest).
2. AEs and concomitant medications, including corticosteroid dose (if applicable) will be recorded.
3. ECG taken (after at least 5 minutes of rest in the supine position) (visit 12 only).
4. Laboratory samples will be collected for:
 - Serum PK sample
 - Serum PD sample

Study drug will be administered by IV infusion over 30 minutes.

After dosing with study drug, the following procedures will be performed:

1. Vital signs will be taken including BP, pulse rate, RR, and temperature (after at least 5 minutes of rest) at the following timepoint: 30 minutes.
2. ECG taken (after at least 5 minutes of rest in the supine position), to be obtained immediately post dose (visit 12 only).
3. Serum PK samples will be taken at the following timepoint: 30 minutes (visit 12 only).
4. Serum PD samples will be taken at the following timepoint: 30 minutes (visit 12 only).
5. At Treatment Visit 12, provide subjects with supplies to collect first void urine samples for urine albumin/creatinine and protein/creatinine ratios on three mornings prior to Follow-Up Visit 1.

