For subjects in Cohort 3, the study will consist of screening (4 weeks), initial treatment (12 weeks) and initial follow-up (6 weeks). Cohort 3 subjects who have 24-hour urine protein $\geq 50\%$ of baseline or > 1000 mg/24 hours at the end of the initial follow-up period (6-week follow-up visit) may elect to receive open-label OMS721 370 mg IV once weekly for 12 additional weeks. Follow-up for all Cohort 3 subjects will be 104 weeks from the first dose of study drug.

Subjects will have two screening visits within a 28-day screening period. Within the screening period and before the first study drug dose, consented subjects will provide three urine samples (collected once daily) on each of two three-consecutive-day periods to establish baseline values of the albumin/creatinine ratio and protein/creatinine ratio. In addition, the subjects will provide one 24-hour urine protein sample to establish baseline values and confirm eligibility.

During the initial 4 weeks of treatment, Cohort 1 subjects will be maintained on their stable pre-study dose of corticosteroids. This initial 4-week treatment period will allow assessment of whether OMS721 can improve measures of renal function when administered to subjects with steroid-dependent disease when co-administered with corticosteroids. Investigators will be instructed to maintain subjects' dose of corticosteroids during the initial 4-week period unless an increase in corticosteroid dose is medically indicated.

At the end of the initial 4-week treatment period, Cohort 1 subjects will undergo corticosteroid taper over 4 weeks. The target will be a taper to ≤ 6 mg prednisone (or equivalent dose) daily. The taper schedule will be at the discretion of the Investigator. Over this period, the taper will be discontinued in subjects who have deterioration of renal function, as determined by the Investigator. Subjects will be treated with OMS721 through the corticosteroid taper and complete 12 weeks of treatment. The taper of steroids and OMS721 treatment will permit assessment of whether OMS721 allows a decrease in the dose of corticosteroid required to maintain stable renal function.

Subjects in Cohort 1 and Cohort 2 will remain in the study for 6 weeks following their last study drug dose. Subjects in Cohort 3 will remain in the study for 104 weeks following their first blinded study drug dose.

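### The 12-week change in 24-hour urine protein has no scheduled sample in the initial course: the first post-baseline collection is at Week 18, and for Cohorts 1 and 2 even that is unclear

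*SAP*

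**What the plan says.** **Endpoint.** SAP Section 6 names "24-hour urine protein change from baseline to 12 weeks" as a secondary endpoint. Protocol 7.3.2 has "Proteinuria from baseline to 12 weeks assessed by 24-hour urine protein collection by disease". The Protocol synopsis gives the endpoint without a time: "Change from baseline in 24-hour urine protein". Protocol 11.1 also gives no time.

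**Baseline.** SAP Section 4 says that in screening "the subjects will provide one 24-hour urine protein sample to establish baseline values and confirm eligibility". Both schedules place its return at Screening Visit 2.

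**After baseline.** In Protocol 19.2 the row "Collect 24-hour Urine protein samples" is marked at Screening Visit 2 and Follow-Up Visit 2 only. SAP 5.1 marks the same two visits and adds the Cohort 3 extended follow-up visits. Neither marks a treatment visit or Follow-Up Visit 1.

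**Visit text.** On the kit for the first follow-up visit, Protocol 10.1.8 reads "At Treatment Visit 12, provide subjects with supplies to collect first void urine samples for urine albumin/creatinine and protein/creatinine ratios on three mornings prior to" that visit; it mentions no 24-hour supplies. Protocol 10.1.9 (Follow-Up Visit 1) then says: "For Cohort 3 subjects only, subjects will be provided with supplies to collect 24-hour urine samples in the week prior to next Follow-Up Visit". Protocol 10.1.10 (Follow-Up Visit 2) does not list a 24-hour urine among its procedures.

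**Analysis.** SAP 12.6 summarises 24-hour urine protein visit by visit and does not say which visit stands for 12 weeks. Protocol 13.2.1.1 uses observed data without imputation. The efficacy population (Protocol 13.2.1.2, SAP 8.3.3) requires a baseline and at least one post-baseline 24-hour urine protein.

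**The concern.** The study title asks about the effect on proteinuria, and 24-hour urine protein is the first-listed efficacy measure. Both documents fix it at 12 weeks, the end of the blinded or open-label initial course. If nothing is collected then, the endpoint as defined is empty, and the analyst must either leave it blank or choose a substitute visit later, possibly with data in hand.

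The first value that does exist is taken about six weeks after the last dose. That answers whether a change persists after stopping, not what the change was at the end of dosing. Protocol 7.2 itself treats persistence as a separate question and added extended follow-up in Cohort 3 to study it.

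A second problem lies underneath. If Cohorts 1 and 2 do not collect the Week 18 sample, their subjects fail the definition of the efficacy population. SAP 9.1 bases all efficacy analyses on that population, so their albumin/creatinine, eGFR and corticosteroid-dose results would be lost with the 24-hour result.

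**Working it through.** The plan gives no figure to reproduce here. The check sets the schedules against the analysis windows.

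**1. Where a 24-hour urine is collected in the initial course**

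| Visit | Nominal day | SAP Table 2 window | Protocol 19.2 | SAP 5.1 |
|---|---|---|---|---|
| Screening Visit 2 | -14 | -20 to -1 | yes | yes |
| Treatment Visits 1 to 11 | 1 to 71 | before Day 75 | no | no |
| Treatment Visit 12 | 78 | 75 to 81 | no | no |
| Follow-Up Visit 1 | 85 | 82 to 102 | no | no |
| Follow-Up Visit 2 | 120 | 103 to 148 | yes | yes |
| Follow-Up Visits 3 to 9 (Cohort 3) | 176 to 722 | from 149 | not marked, but listed in 10.1.11 | yes |

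The Treatment Visit 12 window follows from the Table 2 rule of D - 3 to D + 3: 78 - 3 = 75 and 78 + 3 = 81.

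**2. Which day could be 12 weeks**

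The schedule labels Day 78 as Week 12. Day 85 is (85 - 1)/7 = 12.0 weeks after the first dose, though the schedule labels it Week 13. Neither visit has a 24-hour urine.

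**3. When the first post-baseline sample can fall**

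- Nominal: the week before Day 120 is Days 113 to 119. That is 113 - 78 = 35 to 119 - 78 = 41 days after the last dose.
- With the visit window of plus or minus 3 days: earliest 120 - 3 - 7 = Day 110; latest, counting the visit day itself, 120 + 3 = Day 123. That is 32 to 45 days after Day 78.
- All of Days 110 to 123 lie in 103 to 148. None lies in 75 to 81 or 82 to 102. A conforming sample is therefore always assigned to Follow-Up Visit 2.
- Protocol 7.1 also mentions a visit 4 weeks after the last dose. It is absent from both schedules, and its day (78 + 28 = 106) would also fall in the Follow-Up Visit 2 window.

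Scheduled 12-week values: 0 of about 44 planned subjects.

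**4. Whether re-treatment supplies the value**

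Protocol 10.1.14 does collect a 24-hour urine one week after a re-treatment course. If re-treatment starts no earlier than the first permitted day of Follow-Up Visit 2 (120 - 3 = Day 117), the earliest such visit is 117 + 84 - 3 = Day 198, or (198 - 1)/7 = 28.1 weeks. It follows optional open-label drug, so it cannot be a 12-week value of the initial course.

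**5. Cohorts 1 and 2 at Week 18**

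- For collection: both schedules mark Follow-Up Visit 2 with no cohort limit.
- Against: 10.1.9 gives 24-hour supplies to Cohort 3 only, and 10.1.10 does not list the collection.
- Planned subjects affected: 16 + 10 = 26 of about 44, or 59%. Those who roll over would follow Cohort 3 procedures.

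**6. What can be computed at 12 weeks**

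Both schedules collect the three-morning first-void samples at Follow-Up Visit 1. The albumin/creatinine change to 12 weeks, also a secondary endpoint in SAP Section 6, therefore has data. The protein/creatinine ratio is less clear: Visit 12 dispenses kits for both ratios, but the Follow-Up Visit 1 list in 10.1.9 names only albumin/creatinine.

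**The case against.** The primary endpoint is safety. The study is unpowered (Protocol 13.1, SAP 4.1), no test is planned (SAP 12.3), and no decision rule uses the 12-week value. The synopsis and Protocol 11.1 give no time, so a by-visit change from Week 18 onward meets those statements. An end-of-treatment proteinuria measure also exists in the albumin/creatinine ratio. All of this stands and limits the severity. It does not give the 12-week endpoint any data.

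Three stronger readings are tempting, and the documents do not support them.

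- *A Week 18 value will be reported as a 12-week effect.* SAP 12.6 summarises by visit, and Table 2 labels the sample Follow-Up Visit 2, Day 120. Followed as written, the SAP leaves the 12-week endpoint empty; it does not mislabel the later value.
- *The effect will largely have gone by Week 18.* Protocol 7.2.1 says "The dose level of OMS721 370 mg IV in this study inhibits the lectin pathway for approximately one week", but this concerns pathway inhibition at 370 mg, not proteinuria and not the 4 mg/kg of Cohorts 1 and 2. The documents give no rate at which an effect on proteinuria fades, and Protocol 7.2 reports continued suppression in treated IgAN subjects. No percentage loss can be derived.
- *No 24-hour urine is ever taken at the end of a course.* The Cohort 3 re-treatment follow-up visit has one. The gap concerns the initial course.

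**Conclusion.** The concern holds. The 12-week change in 24-hour urine protein, as defined in Protocol 7.3.2 and SAP Section 6, has no scheduled data in any cohort. Only a by-visit summary starting at Week 18, six weeks after the last dose, can be produced.

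For Cohorts 1 and 2 the documents conflict on whether even the Week 18 sample is collected. If the visit text governs, up to 26 of about 44 planned subjects have no scheduled post-baseline 24-hour value and fall outside the efficacy population, apart from any who roll over. If the schedules govern, this second problem disappears and the first remains.

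The conclusion assumes that samples are taken as the protocol instructs and that the last initial dose is on its nominal Day 78. It needs no assumption about how long an effect on proteinuria lasts. Severity is should-fix: a named efficacy endpoint is wrong as written, but it is secondary in a descriptive study.

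**What to change.** 1. **Restate the endpoint.** In Protocol 7.3.2 and SAP Section 6, define the 24-hour endpoint as change from baseline to Week 18 (Follow-Up Visit 2), and describe it as a post-treatment value. State the same visit in SAP 12.6 and add the time to the synopsis and Protocol 11.1.
2. **Settle Cohorts 1 and 2.** Reconcile Protocol 10.1.9 and 10.1.10 with Protocol 19.2 and SAP 5.1. Either make it explicit that these cohorts collect the Week 18 sample, or limit the 24-hour endpoint to Cohort 3 and redefine the efficacy population for Cohorts 1 and 2 so that it does not depend on that sample. Step 1 alone is not enough without this.
3. **Name the 12-week measure.** State that 12-week proteinuria is assessed by the albumin/creatinine ratio at Follow-Up Visit 1 (Day 85), already a secondary endpoint, with the protein/creatinine ratio in support and still exploratory. Add protein/creatinine to the Follow-Up Visit 1 list in 10.1.9.

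Steps 1 and 3 cost wording only, and the claim about 24-hour protein becomes narrower. Step 2 is also wording if the sample is already being collected or the endpoint is limited to Cohort 3; otherwise it adds one home collection per remaining Cohort 1 or 2 subject. If the sponsor wants a true end-of-treatment 24-hour value, that is a separate option: one more home collection per subject, with supplies given at Treatment Visit 12 alongside the first-void kit.
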